## **5.4 Duration of Therapy**

**5.4.1** Enzalutamide - 6 (28 +/-3 days) cycles-expected

**5.4.2** External beam radiation up to 11 weeks-expected

**5.4.3** Treatment will continue for 6 (28 day) cycles or until one of the following criteria applies:

- Disease progression;
- Intercurrent illness that prevents further administration of treatment;
- Unacceptable adverse event(s);
- Participant demonstrates an inability or unwillingness to comply with the oral medication regimen and/or documentation requirements;
- Participant decides to withdraw from the study; or
- General or specific changes in the participant's condition render the participant unacceptable for further treatment in the opinion of the treating investigator.

## **5.5 Duration of Follow-up**

**5.5.1** Patients will be followed on study for 3 months after treatment (cessation of enzalutamide). Additional follow-up to assess the status of the cancer will be conducted at the discretion of the treating physicians

**5.5.2** In the event a patient discontinues enzalutamide due to a related adverse event, follow up will continue until adequate resolution of the adverse event, the physician deems the adverse event to be stable, the patient initiates another systemic antineoplastic drug or an investigational drug, or the patient withdraws consent from the study.

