**Timeline**

\* Fiducial placement and biopsy 3-7 weeks after initiating enzalutamide    \*\*

Radiation initiated 7-10 weeks after initiating enzalutamide.

\*\*\* Patients that are unable to complete enzalutamide therapy will still be treated with EBRT per SOC

\*\*\*\* 28 day cycle allows for +/- 3 day window

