### 5.2 Agent Administration

5.2.1 Treatment will be administered on an outpatient basis. Expected toxicities and potential risks as well as dose modifications for enzalutamide are described in Section 6 (Expected Toxicities and Dosing Delays/Dose Modification). No investigational or commercial agents or therapies other than those described below may be administered with the intent to treat the participant's malignancy.

CONFIDENTIAL

This document is confidential. Do not disclose or use except as authorized.

Version 13.0 Protocol Version Date: 1/09/2015

5.2.2 Patients will be treated in 6 (28 +/- 3 days) cycles. EBRT will be initiated 7-10 weeks into enzalutamide therapy. Patients will be seen every 28 (+/- 3 days) days for history and physical, adverse event and concomitant medication assessment. At these visits routine laboratory parameters will be obtained and a subset of these must be reviewed prior to dispensing the investigational agent. The routine laboratories at the beginning of each cycle should be completed per the Study Calendar in section 8.

The criteria to treat at the beginning of each cycle are:

- ANC greater than 1,000mm^3
- Hgb greater than 8.0 g/dL
- Platelets greater than or equal to 50,000
- ALT less than 3.5x upper limit normal
- AST less than 3.5x upper limit normal

Any grade (3 or greater) non-hematologic adverse event (such as fatigue, etc.) must be resolved to (grade 1 or less) in order to continue therapy. The Medical Monitor should be notified of any adverse events that require holding, stopping or dose modifications of study drug.

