##### Rare

- Rash
- Neutropenia (grade 3 and 4)
- Short term memory loss

Evidence of seizure will result in cessation of enzalutamide and withdrawal from the study. Other Grade 3 or 4 possibly-related non-hematologic toxicity, including fatigue, may result in dose reduction. Based upon experience from Phase 3 studies enzalutamide is generally well tolerated. The most common adverse events related to enzalutamide include fatigue and nausea. Any dose reduction of enzalutamide requires consultation with the Medical Monitor. Instructions on dose reduction for various toxicities are provided below (section 6.2):

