#### 6.2.2 Management of enzalutamide toxicity

6.2.2.1 If Grade 1–2 toxicities occur, give supportive care per institutional guidelines. No enzalutamide dose reduction should occur. However, at the discretion of the treating physician, an investigator can hold enzalutamide for intolerable Grade 2 toxicity for a maximum of 14 days. Participants should resume enzalutamide at the original dose (160 mg/day). If the participant is not able to resume study medication after being held for 14 days, the participant must be permanently removed from the study.

6.2.2.2 If Grade 3 fatigue occurs, hold enzalutamide and contact the medical monitor for appropriate instructions on dose reduction.

6.2.2.3 If Grade 3 or higher toxicities occur that are considered potentially related to enzalutamide including headache (that interferes with activities of daily living [ADL]), nausea (requiring total parenteral nutrition or intravenous fluids), vomiting (> 6 episodes/24 hours requiring total parenteral nutrition or intravenous fluids), diarrhea (requiring intravenous fluids or hospitalization, or resulting in hemodynamic collapse), or any other toxicity where patient safety is jeopardized, hold enzalutamide. When the toxicity has resolved to ≤ Grade 1, resume study medication at the full dose. Prophylactic medications should be considered as appropriate. If toxicity recurs, hold study medication and adjust or add medications to mitigate the toxicity. When the recurrent toxicity has resolved to ≤ Grade 1, resume enzalutamide at 120 mg/day (3 pills /day). This should be done with the approval of the PI and the medical monitor.

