### 9.2 Secondary endpoints

#### 9.2.1. Safety and Tolerability

Safety and tolerability will be documented throughout the study by assessment of adverse events, vital signs and laboratory assessments as defined in the Schedule of Activities (Section 8). Adverse events will be graded according to the National Cancer Institute Common Terminology Criteria for Adverse Events, Version 4.03 (NCICTCAE v4.03). Only toxicity with attribution of possibly, probably or definitely ('treatment-related') will be reported. Adverse events will be monitored and recorded until the safety follow-up visit (3 months after the completion of the drug therapy). Any glucose tests collected under previous protocol amendments will not be assessed for adverse events.

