## **10.4 Reporting to the Study Sponsor 10.4.1**

### **Serious Adverse Event Reporting**

All serious adverse events that occur after the initial dose of study treatment, during treatment, or within 30 days of the last dose of treatment must be reported to the DF/HCC Overall Principal Investigator on the local institutional SAE form. This includes events meeting the criteria outlined in Section 10.1.2, as well as the following:

- Grade 2 (moderate) and Grade 3 (severe) Events – Only events that are unexpected and possibly, probably or definitely related/associated with the intervention.
- All Grade 4 (life-threatening or disabling) Events – Unless expected AND specifically listed in the protocol as not requiring reporting.
- All Grade 5 (fatal) Events – When the participant is enrolled and actively participating in the trial OR when the event occurs within 30 days of the last study intervention.

Note: If the participant is in long term follow up, report the death at the time of continuing review.

Participating investigators must report each serious adverse event to the DF/HCC Overall Principal Investigator as well as the Astellas Safety Department within 24 hours of learning of the occurrence. In the event that the participating investigator does not become aware of the serious adverse event immediately (e.g., participant sought treatment elsewhere), the participating investigator is to report the event within 24 hours after learning of it and document the time of his or her first awareness of the adverse event. Report serious adverse events by telephone, email or facsimile both to:

DF/HCC Overall Principal Investigator and Medical Monitor:

[name]  
[[contact]](mailto:[contact])  
[contact]  
[contact]

Astellas Safety Department:

Astellas Pharma Global Development – United States  
Email: [[contact]](mailto:[contact])  
[contact]

Within the following 24-48 hours, the participating investigator must provide follow-up information on the serious adverse event. Follow-up information should describe whether the event has resolved or continues, if and how the event was treated, and whether the participant will continue or discontinue study participation.

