#### **10.8 Monitoring of Adverse Events and Period of Observation**

All adverse events, both serious and non-serious, and deaths that are encountered from initiation of study intervention, throughout the study, and within 30 days of the last study intervention should be followed to their resolution, or until the participating investigator assesses them as stable, or the participating investigator determines the event to be irreversible, or the participant is lost to follow-up. The presence

Version 13.0 Protocol Version Date: 1/09/2015  
and resolution of AEs and SAEs (with dates) should be documented on the appropriate case report form and recorded in the participant's medical record to facilitate source data verification.

For some SAEs, the study sponsor or designee may follow-up by telephone, fax, and/or monitoring visit to obtain additional case details deemed necessary to appropriately evaluate the SAE report (e.g., hospital discharge summary, consultant report, or autopsy report).

Participants should be instructed to report any serious post-study event(s) that might reasonably be related to participation in this study. Participating investigators should notify the DF/HCC Overall Principal Investigator of greater or equal to grade 3 events and the IRB of any unanticipated death or adverse event occurring after a participant has discontinued or terminated study participation that may reasonably be related to the study.

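### For men who stop enzalutamide early, the safety-collection rules conflict and can leave toxicity during radiotherapy uncollected

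*Combined protocol and SAP*

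**What the plan says.** Five places set the end of safety collection:

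- Section 5.5.1: "Patients will be followed on study for 3 months after treatment (cessation of enzalutamide".
- Section 9.2.1: "Adverse events will be monitored and recorded until the safety follow-up visit (3 months after the completion of the drug therapy".
- Section 10.4.1, on serious adverse events (SAEs) after the first dose, during treatment, or "within 30 days of the last dose of treatment must be reported to the DF/HCC Overall Principal Investigator". The report is due within 24 hours.
- Section 10.8, on all adverse events and deaths from the start of intervention and "within 30 days of the last study intervention should be followed to their resolution".
- The Section 8 calendar. As it reads, the row for adverse events and concomitant medication has its last mark at the end of cycle 6 and none at the 3-month visit.

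On timing, Section 5.2.2 says "EBRT will be initiated 7-10 weeks into enzalutamide therapy". A schema footnote adds: "Patients that are unable to complete enzalutamide therapy will still be treated with EBRT per SOC".

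On leaving the study, Section 6.1.3 says "Evidence of seizure will result in cessation of enzalutamide and withdrawal from the study". Under 6.2.2.1, if enzalutamide is held for intolerable Grade 2 toxicity and cannot be resumed after 14 days, "the participant must be permanently removed from the study". Section 6.3 discontinues from the study a man who misses 14 days of drug in total. Against this, 5.5.1 sets follow-up for patients generally. Section 5.5.2 continues it after a stop for a related adverse event, until that event resolves or is stable, another anticancer or investigational drug is started, or consent is withdrawn.

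**The concern.** For a man who takes all six cycles the different end points do no harm, because EBRT is finished before enzalutamide ends. For a man who stops early the order can reverse: the last capsule comes first and most or all of the radiotherapy follows. A clock that starts at the last capsule can then run out before or during EBRT, and a man classed as off study may have no scheduled safety collection during EBRT at all. A site cannot both remove him from the study and keep him in on-study follow-up.

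Safety and tolerability is a secondary objective, EBRT toxicities are listed as expected in 6.1.2, and 13.2.2 reports grade 3 or higher treatment-related events in all 71 treated patients. If EBRT-period events are not collected in some men, those men still sit in the denominator, and they are disproportionately men who stopped because of toxicity. The 24-hour SAE duty could also lapse while radiotherapy described in the protocol is still being given.

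**Working it through.** **The plan's own safety figures.** Section 13.2.2 gives a 97% chance of seeing a toxicity with a true rate of 5%, and a maximum 90% interval width of 21%, for 71 patients. 1 − 0.95^71 = 0.974, and the exact (Clopper-Pearson) maximum width is 20.6%. Both agree.

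**Inputs** (weeks from first enzalutamide dose)

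- EBRT start: week 7 to 10 (5.2.2).
- Fractions: 75.6/1.8 = 42 to 79.2/1.8 = 44 (5.2.3.1).
- Five fractions a week is an assumption. Uninterrupted length is then 42/5 = 8.4 to 44/5 = 8.8 weeks.
- Longest expected course: 11 weeks (5.4.2). Section 6.3 gives nine and a half weeks. The two need reconciling, and I use the longer.
- SAE window: 30/7 = 4.29 weeks. Three months is taken as 13 weeks.

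**End of EBRT.** Earliest 7 + 8.4 = 15.4. Latest uninterrupted 10 + 8.8 = 18.8. Latest at 11 weeks 10 + 11 = 21.

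**If the 30 days run from the last enzalutamide dose**

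| Last dose (week) | SAE window closes | EBRT outside, start week 7 (ends 15.4) | EBRT outside, start week 10 (ends 18.8) | 3-month window closes |
|---|---|---|---|---|
| 4 | 8.3 | 7.1 weeks | all 8.8 weeks | 17 |
| 6 | 10.3 | 5.1 weeks | 8.5 weeks | 19 |
| 11.1 | 15.4 | none | 3.4 weeks | 24.1 |
| 14.5 | 18.8 | none | none | 27.5 |
| 24 (full course) | 28.3 | none | none | 37 |

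The SAE window reaches the end of EBRT only if the last dose is at or after 15.4 − 4.29 = 11.1, 18.8 − 4.29 = 14.5, or 21 − 4.29 = 16.7 for the 11-week course from week 10.

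**If the 3-month window is kept.** It reaches the end of EBRT if the last dose is at or after 15.4 − 13 = 2.4, 18.8 − 13 = 5.8, or 21 − 13 = 8.

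- A week-6 stop is followed to week 19, which covers any uninterrupted course (15.4 to 18.8) but not an 11-week course from week 10 (21 − 19 = 2 weeks short).
- A week-4 stop is followed to week 17, which covers EBRT from week 7 but falls 18.8 − 17 = 1.8 weeks short for EBRT from week 10.

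**If the man is off study.** Three provisions remain:

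- 5.5.2 follow-up of the related event that caused the stop.
- Possible contact about toxicity still present at the off-study visit (6.3).
- The post-study part of 10.8, which covers events that may reasonably be related to the study. It asks participants to report serious ones and investigators to notify the overall investigator of those of grade 3 or higher.

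None of these schedules collection of new events through EBRT.

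**Effect on precision.** If 7 of 71 men (assumed for illustration) had no EBRT-period data, n = 64 gives 1 − 0.95^64 = 0.962 and a maximum width of 21.8%. Precision hardly moves. The issue is which men are missing.

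**The case against.** The strongest reply is that the SAE gap rests on one reading. Section 10.4.1 speaks of treatment, and 10.8 (like the fatal-event item in 10.4.1) of study intervention. Elsewhere the protocol names enzalutamide when it means the drug alone, as in 5.3.1.1 and 5.5.1. EBRT appears under treatment in the schema, in the treatment plan (5.2.3) and under duration of therapy (5.4.2). If EBRT counts, the 30 days run past the last fraction and there is no SAE gap. This stands as a possible reading. The footnote calling EBRT standard of care for these men, and the enzalutamide anchor in 5.3.1.1, 5.5.1 and 9.2.1, point the other way. The text does not settle it, so sites may apply different clocks.

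A reader might infer that the radiotherapy of early stoppers goes largely unobserved. The documents do not support that: with the 3-month window kept, a week-6 stop has adverse-event recording through any uninterrupted course. Nor does all follow-up vanish once a man is off study, because 5.5.2, 6.3 and 10.8 each leave something. They narrow the gap without closing it.

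It is also fair that not every toxicity stop removes a man from the study. The triggers are a seizure, a hold for intolerable Grade 2 toxicity not resumed after 14 days, and 14 missed days. The stopping list in 5.4.3 ends treatment, not participation. And 30-day SAE reporting and 3-month event recording serve different purposes, so their different lengths are not in themselves a contradiction.

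**Conclusion.** The point holds as a conflict in the rules that can leave EBRT toxicity uncollected in some early stoppers. It should be corrected, but it does not touch the primary endpoint, for which 13.1 already counts early discontinuation as failure.

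The 5.1 to 8.5 weeks outside SAE reporting after a week-6 stop assumes that the 30 days run from enzalutamide and that five fractions are given weekly. The wider gap applies only if a man is treated as off study, and there the sections contradict each other.

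A reader might infer that every early stopper is affected. That does not follow: even on the enzalutamide reading there is no SAE gap once the last dose is at or after about week 11.1 to 16.7, depending on the EBRT course. The documents give no early-stop rate, so the number cannot be calculated; it is likely small. As a rough guide to one trigger, the 7 seizures in 800 men cited in 2.1.1 would correspond to 71 × 7/800 = 0.6 men here.

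A reader might also infer a known downward bias in the grade 3 or higher rates. Uncollected events could only lower the count, and the loss would be selective, but the size cannot be estimated. Only treatment-related events are reported, and whether radiotherapy given as standard of care after enzalutamide counts as study treatment for attribution is not stated.

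**What to change.** Use one anchor in 5.5.1, 9.2.1, 10.4.1, 10.8 and the calendar's adverse-event row: adverse events to 3 months, and SAEs to at least 30 days, after the later of the last enzalutamide dose and the last EBRT fraction. On the EBRT dates above, the 30 days for an early stopper would then end at week 15.4 + 4.29 = 19.7, 18.8 + 4.29 = 23.1, or 21 + 4.29 = 25.3. For a man who completes enzalutamide at week 24 the anchor does not move.

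Reconcile the off-study wording in 6.1.3, 6.2.2.1 and 6.3 with 5.5.1 and 5.5.2, so that coming off enzalutamide does not end safety data collection unless consent is withdrawn. Add the missing adverse-event mark at the calendar's 3-month visit.

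This changes data collection only. It alters no treatment or stopping rule. The cost is amendment wording, plus adverse-event and SAE collection for a few early stoppers, who attend for EBRT anyway.

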# **6. EXPECTED TOXICITIES AND DOSING DELAYS/DOSE MODIFICATIONS**

## **6.1.1 Fiducial placement for prostate tracking during external beam +/- biopsy**

**Likely:**

- Discomfort from the placement of needles into the prostate for fiducial placement and biopsy
- Minor Rectal bleeding

CONFIDENTIAL

This document is confidential. Do not disclose or use except as authorized.

Version 13.0 Protocol Version Date: 1/09/2015

**Rare:**

- Significant bleeding requiring transfusion and/or hospitalization  Infection

**Extremely Rare:**

- Massive bleeding
- Death

### **6.1.2 External Beam Radiation**

#### **6.1.2.1 Acute Reaction**

**Common**

- Urinary frequency
- Dysuria
- Increase bowel frequency
- Exacerbation of hemorrhoids

**Uncommon**

- Significant fatigue

**Rare**

- Diarrhea
- Rectal bleeding
- Skin erythema
- Urinary obstruction

#### **6.1.2.2 Late Reaction**

**Common**

- Dry ejaculation
- Erectile dysfunction
- Sterility

**Uncommon**

- Rectal mucous discharge
- Rectal bleeding

**Rare**

- Gross hematuria
- Chronic diarrhea

CONFIDENTIAL

This document is confidential. Do not disclose or use except as authorized.

Version 13.0 Protocol Version Date: 1/09/2015

- Rectal bleeding requiring management

### **Extremely Rare**

- Significant rectal bleeding requiring transfusion
- Radiation induced damage of normal tissues requiring surgery
- Second cancers
- Death

#### **6.1.3 Enzalutamide**

##### Common

- Peripheral Edema
- Flushing
- Diarrhea
- Neutropenia
- Arthralgia
- Musculoskeletal pain
- Fatigue
- Gynecomastia

##### Serious

- Seizure
- Spinal cord compression
- Infectious disease

##### Rare

- Rash
- Neutropenia (grade 3 and 4)
- Short term memory loss

Evidence of seizure will result in cessation of enzalutamide and withdrawal from the study. Other Grade 3 or 4 possibly-related non-hematologic toxicity, including fatigue, may result in dose reduction. Based upon experience from Phase 3 studies enzalutamide is generally well tolerated. The most common adverse events related to enzalutamide include fatigue and nausea. Any dose reduction of enzalutamide requires consultation with the Medical Monitor. Instructions on dose reduction for various toxicities are provided below (section 6.2):

## **6.2 TOXICITY MANAGEMENT**

### 6.2.1 Management of Radiation Toxicity

#### 6.2.1.1 Urinary

CONFIDENTIAL

This document is confidential. Do not disclose or use except as authorized.

Version 13.0 Protocol Version Date: 1/09/2015

6.2.1.1.1 Symptomatic urinary medicines, such alpha blockers for decreased urinary flow  
6.2.1.1.2 NSAIDS for dysuria if no contraindication.

#### 6.2.1.2 Rectal

6.2.1.2.1 Low fiber diet  
6.2.1.2.2 Loperamide at the discretion of the treating physician.

#### 6.2.1.3 Management of gynecomastia

At the discretion of the treating physician, at any time before or during treatment patients are permitted to receive radiation therapy to the breasts to prevent or treat gynecomastia. Treatments such as tamoxifen are not permitted for gynecomastia.

#### 6.2.2 Management of enzalutamide toxicity

6.2.2.1 If Grade 1–2 toxicities occur, give supportive care per institutional guidelines. No enzalutamide dose reduction should occur. However, at the discretion of the treating physician, an investigator can hold enzalutamide for intolerable Grade 2 toxicity for a maximum of 14 days. Participants should resume enzalutamide at the original dose (160 mg/day). If the participant is not able to resume study medication after being held for 14 days, the participant must be permanently removed from the study.

6.2.2.2 If Grade 3 fatigue occurs, hold enzalutamide and contact the medical monitor for appropriate instructions on dose reduction.

6.2.2.3 If Grade 3 or higher toxicities occur that are considered potentially related to enzalutamide including headache (that interferes with activities of daily living [ADL]), nausea (requiring total parenteral nutrition or intravenous fluids), vomiting (> 6 episodes/24 hours requiring total parenteral nutrition or intravenous fluids), diarrhea (requiring intravenous fluids or hospitalization, or resulting in hemodynamic collapse), or any other toxicity where patient safety is jeopardized, hold enzalutamide. When the toxicity has resolved to ≤ Grade 1, resume study medication at the full dose. Prophylactic medications should be considered as appropriate. If toxicity recurs, hold study medication and adjust or add medications to mitigate the toxicity. When the recurrent toxicity has resolved to ≤ Grade 1, resume enzalutamide at 120 mg/day (3 pills /day). This should be done with the approval of the PI and the medical monitor.

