## 1. OBJECTIVES

### 1.1 Study Design

The goal of this exploratory study is to assess efficacy of adding enzalutamide in the neoadjuvant and adjuvant setting in combination with external beam radiation therapy (EBRT). The population will be prostate cancer patients with intermediate risk prostate cancer, choosing radiation therapy as their primary form of therapy. This is a phase II single arm trial that has as its primary objective to estimate the proportion of patients with PSA  $\leq 0.2$  ng/ml at the completion of therapy. This endpoint has been shown to be predictive of long term response in a similar risk-group of patients treated with radiation therapy and LHRH agonists. Secondary endpoints include measurement of serum hormone levels, health-related quality of life (HRQoL) and body fat measurements. It is expected that enzalutamide therapy in contrast to LHRH agonists has a much better profile for these secondary outcomes. Correlative studies will center on understanding enzalutamide's mechanism of action. Data from this trial, if convincing, would lead to a Phase III randomized trial comparing LHRH agonists to enzalutamide as neoadjuvant and adjuvant therapy in combination with EBRT.

On this study patients will be treated with 6 months of Xtandi (enzalutamide). Approximately one-third of the way through this treatment they will receive EBRT. Starting on Day 1, all patients will ingest enzalutamide **160 mg/day** at the same time each day without breaks (except as outlined for toxicity), with or without food, for 6 (28 day +/-3 days) cycles. Dose reduction of enzalutamide to 120 mg/day is allowed with the approval of the Medical Monitor, [name] (Section 6.2.2.3). Patients will be instructed to return all unused capsules at each study visit to assess compliance and will receive study drug every 28 days (+/-3 days) for 6 cycles (24 weeks).

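### The restart dose in Section 6.2.2.1 makes no exception for a man already reduced to 120 mg/day, so read literally it undoes an approved reduction (minor, rare)

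*Combined protocol and SAP*

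**What the plan says.** Section 6.2.2.1 rules out dose reduction for Grade 1–2 toxicity but lets the investigator hold drug for up to 14 days for intolerable Grade 2 toxicity. It then says: "Participants should resume enzalutamide at the original dose (160 mg/day".

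Section 6.2.2.2 covers Grade 3 fatigue: "hold enzalutamide and contact the medical monitor for appropriate instructions on dose reduction".

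Section 6.2.2.3 covers Grade 3 or higher toxicity potentially related to enzalutamide. After a first event: "When the toxicity has resolved to ≤ Grade 1, resume study medication at the full dose". After a recurrence: "resume enzalutamide at 120 mg/day (3 pills /day", with approval from the principal investigator and the medical monitor.

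Two other sections control the way down. Section 1.1: "Dose reduction of enzalutamide to 120 mg/day is allowed with the approval of the Medical Monitor". Section 6.1.3: "Any dose reduction of enzalutamide requires consultation with the Medical Monitor".

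Section 5.2.2 says that a Grade 3 or higher non-hematologic event "must be resolved to (grade 1 or less) in order to continue therapy". It adds: "The Medical Monitor should be notified of any adverse events that require holding, stopping or dose modifications of study drug". Section 6.3.1 takes a man off study once he has missed 14 days of drug in total.

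**The concern.** The protocol foresees men on 120 mg/day, yet the restart sentence in Section 6.2.2.1 prints 160 mg/day for every participant. Going down requires the Medical Monitor. The printed return to 160 mg/day requires nobody's agreement. A site that follows the text would therefore cancel a safety reduction because of an unrelated and milder event. What is at stake is the tolerability of treatment for an individual man, not the primary analysis.

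**Working it through.** The plan gives no figure to reproduce here. The check is a reading of the dosing rules side by side, followed by two short calculations on frequency and size.

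**Step 1. Can a man be on 120 mg/day?** Yes, by two routes: the monitor's instruction after Grade 3 fatigue (6.2.2.2), which can follow a single episode, or recurrence of a Grade 3 or higher toxicity (6.2.2.3).

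**Step 2. What restart dose is printed if he is held again?**

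| Dose before the hold | Reason for the hold | Printed restart dose |
|---|---|---|
| 160 mg/day | Intolerable Grade 2 | 160 mg/day (6.2.2.1) |
| 120 mg/day | Intolerable Grade 2 | 160 mg/day (6.2.2.1, no exception) |
| 120 mg/day | Same Grade 3+ toxicity recurs | 120 mg/day (6.2.2.3) |
| 120 mg/day after Grade 3 fatigue | First Grade 3 headache | Depends on the reading of 6.2.2.3 |

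The second row is the clear case. Grade 3 fatigue leads to a hold and, on the monitor's instruction, 120 mg/day. A later hold for Grade 2 diarrhea (listed as common in 6.1.3) then restarts at 160 mg/day as written.

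In the fourth row, 6.2.2.3 does not say whether recurrence means the same toxicity or any Grade 3+ toxicity. If it means the same toxicity, or if fatigue is handled wholly under 6.2.2.2, the headache is a first event and the full dose applies. If any Grade 3+ toxicity counts, the headache is a recurrence and 120 mg/day applies.

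**Step 3. Does another section supply the missing dose?** No. Section 5.2.2 says when therapy may continue and that the monitor should be told, not at what dose to restart. Section 6.3.1 limits missed drug. The pill diary in Appendix H is printed for 160 mg and 4 capsules a day.

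**Step 4. How often?** Section 2.1.1 reports fatigue dose reductions in 0 of 58 patients at 30, 60 or 150 mg/day, and 0% Grade 3 fatigue at 150 mg/day.

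- Exact one-sided 95% upper limit for 0 of n: 1 − 0.05^(1/n). With n = 58: 1 − 0.05^(1/58) = 0.0503, or 5.0%.
- Applied to the 71 men to be enrolled: 71 × 0.0503 = 3.6 men.
- At a one-sided 97.5% level: 1 − 0.025^(1/58) = 6.2%, and 71 × 0.0616 = 4.4 men.

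These limits assume that the rate in the earlier advanced-cancer study carries over. They pool doses that are all below 160 mg/day, and they cover reductions for fatigue only. On the fatigue route, an affected man must also have a second hold while on 120 mg/day. The first hold must last until Grade 1 or less (5.2.2), and the two together must stay short of 14 missed days (6.3.1). The number affected by that route is therefore smaller than the number reduced.

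**Step 5. How large is the step?** Four 40 mg capsules instead of three: 160/120 = 1.33, or +33%. Section 2.1.1 expects a mean steady-state trough of 12 ± 4 µg/mL at 160 mg/day. With the linear pharmacokinetics stated there, the trough at 120 mg/day is 12 × 120/160 = 9 µg/mL, a difference of 3 µg/mL.

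**The case against.** The strongest reply is that the sentence was not written for reduced men. It follows directly on a ban on reducing the dose for Grade 1–2 toxicity, so it most naturally means that a Grade 2 hold is no reason to come back at less than the starting dose. A reader might infer that the protocol intends to re-escalate reduced men. The documents do not support that; this looks like an omission in drafting. Likely intent does not remove the problem, however, because the number is printed and applies to participants without distinction.

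The monitor is also well placed to catch the case. The monitor is to be notified of every hold, must agree to every reduction, and may state the dose to keep when giving instructions after Grade 3 fatigue. This stands as a mitigation, but notification is not approval and no section sets the dose. A reader might infer that two sites would restart the same kind of patient differently. With central notification of holds, that is speculation.

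A reader might also take the Grade 3 headache route to be as firm as the Grade 2 route. It is not, since it turns on how recurrence in 6.2.2.3 is read.

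Finally, +33% might be read as a demonstrated hazard. It is not. The dose returned to is the standard study dose, below the maximum tolerated dose of 240 mg/day in Section 2.1.1, and the 3 µg/mL difference is smaller than the ± 4 quoted with the mean. The same section does say that fatigue rose with dose and that symptoms resolved after reduction, so harm in a man who has already shown intolerance cannot be excluded.

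**Conclusion.** The point holds as a minor and rare matter of patient safety. It is firm for Section 6.2.2.1 and conditional for Section 6.2.2.3. It rests on reading the restart sentence literally and on the absence of any other rule for a man already at 120 mg/day. The figure of about 5% (under 4 of 71 men) is an upper limit on fatigue reductions, not an estimate of men affected, and it depends on an earlier population carrying over. The primary endpoint, sample size and error rates in Section 13.1 are untouched.

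**What to change.** In 6.2.2.1, replace the reference to the original 160 mg/day dose with *at the dose taken before the hold*. In 6.2.2.3, make the same replacement for the full-dose restart after a first event. Keep the step-down to 120 mg/day on recurrence. Add one sentence: *Any return from 120 to 160 mg/day requires Medical Monitor approval.* This leaves the monitor's discretion under 6.2.2.2 intact.

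The cost is two phrases and one sentence in the next amendment, with no extra visits, tests or patients.
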